7.2 Measuring outcomes

Table 2 summarises what measures are assessed at baseline, 6 and 12 month time-points. Further details about outcome measures are provided above in section 6.2. The Patient Global Impression of Severity (PGI-S) (single-item participant rating of condition severity, with 4 responses from "normal" to "severe") will be included in the baseline questionnaire in place of the PGI-I [34]. Data on intervention fidelity will be gathered at each PFMT appointment by the treating clinician who will review the participant's PFMT/pessary diary and record fidelity to PFMT and pessary use (where appropriate).

Outcome data will be collected from participants mainly using participant-completed questionnaires administered via post, e-mail and telephone as required. If a questionnaire is not returned after the first request, two further requests will be made by the Trial Office. The first reminder will be by email/letter based on the participant's preference. The second reminder will be by phone, and if the participant agrees the data will be collected over the phone. Gift vouchers to the value of £10 will be sent to participants with their 12 month questionnaire.

Table 2. Overview of trial outcome measure data collection

| Data collected | Time-point | | | |
|---|--------------|--------------------------------|-------------|--|
| | Baseline | 6 months* | 12 months* | |
| Primary Outcome | | | | |
| Pelvic floor symptoms (PFDI-20) | Q | Q | Q | |
| Secondary Outcomes | | | | |
| Condition-specific quality of life (PFIQ-7) | Q | Q | Q | |
| Patient Global Impression of Improvement (PGI-I) | Q (PGI-S) | Q | Q | |
| Sexual function (ICIQ-VS Sexual Matters subscale) | Q | Q | Q | |
| Uptake of other prolapse treatment | | Q | Q | |
| Self-efficacy for treatment | Q | Q | Q | |
| Intervention adherence (PFMT + pessary) | | opointments 1-4 & uestionnaire | Q | |
| Pelvic floor muscle strength / function (MOS) | С | | C (blinded) | |
| Prolapse severity (POP-Q) | Cs | | C (blinded) | |
| Economic outcomes | | | | |
| General health-related quality of life (EQ-5D-5L) | Q | Q | Q | |
| Healthcare utilisation questionnaire | Q | Q | Q | |

^{*} women in the PFMT plus pessary group will have a pessary review appointment at 2 weeks before they receive their 6 and 12 month questionnaires at which the pessary will be removed (if they are still

IRAS ID: 338183 PEPPY protocol version 3.0 26/02/2025 ISRCTN: xxxxxx Page 22 of 51

using a pessary). Q - Data gathered in self-report questionnaire C - Data gathered during vaginal examination in clinic s simple version of the POP-Q.

7.3 Baseline appointment

A Baseline CRF will be completed at the baseline appointment including relevant participant details and information required for randomisation (e.g. age, height, weight, medical history, assessment of vaginal tissues, prolapse severity, pelvic floor muscle strength and function). Participants will be randomised and complete the baseline questionnaire. PFMT treatment will then begin and the treating physiotherapist will record the prescribed PFMT and add it to the participant's exercise diary for their information.

7.4 Follow-up

6 month follow-up

The 6 month questionnaire will be posted or emailed to participants for completion. Women using a pessary will be asked to pause pessary use 2 weeks before completion of this questionnaire. An appointment for pessary removal will be arranged if required.

12 month follow-up

The 12 month questionnaire will be posted or emailed to participants for completion. Women using a pessary will be asked to pause pessary use 2 weeks before completion of this questionnaire. An appointment for pessary removal will be arranged if required. Participants will attend a 12 month appointment for blinded assessment of pelvic floor muscle strength/function and prolapse severity.

7.5 Change of Status/Withdrawal procedures

Participants remain in the trial unless they choose to withdraw consent. Participants are free to withdraw from the trial at any timepoint. All changes in status, with the exception of complete withdrawal of consent, mean the participant is still followed up for all trial outcomes wherever possible. All data collected up to the point of complete withdrawal is retained and used in the analysis.

Following informed consent, if a participant loses capacity, the consent given when capable remains legally valid. In such circumstances, identifiable data collected with consent will be retained and used in the study but no further data will be collected or research procedures carried out.

Participants who do not receive their allocated treatment or receive the other (non-allocated) intervention or discontinue their healthcare management are not considered withdrawals and will be followed-up for all trial outcomes unless they request otherwise. One of the outcomes is treatment received. This is a pragmatic study and will monitor accruing data on treatment initiated and continued during the study which will inform the proportion of participants continuing in the two randomised treatment pathways.

Participants who request that no further questionnaires are issued (i.e. completing questionnaires) will be followed up for other trial outcomes unless they are complete withdrawals.

Participants for whom any outcome data are available are included in an intention to treat analysis.

7.6 Data processing

The local research team staff will enter locally collected data in the centres. Staff in the Trial office will work closely with the local research team to ensure the data are as complete and accurate as possible. Postal questionnaires will be entered into the study website by trial office staff.

IRAS ID: 338183 PEPPY protocol version 3.0 26/02/2025 **ISRCTN: xxxxxx** Page 23 of 51

7.7 Long term follow-up

We plan to seek funding to follow-up participants in the longer-term using data from NHS and other government central registries, and GP and hospital notes. We seek informed consent for this at the outset of the trial.

8. **SAFETY**

8.1 **Definitions**

| Term | Standard definition |
|--------------------------------|---|
| Adverse Event (AE) | Any untoward medical event affecting a clinical trial participant. |
| Serious Adverse Event (SAE) | Where an AE: results in death; is life threatening (i.e. the subject was at risk of death at the time of the event; it does not refer to an event which hypothetically might have caused death if it were more severe); requires hospitalisation or prolongation of existing hospitalisation; results in persistent or significant disability or incapacity; is a congenital anomaly or birth defect, is otherwise considered medically significant by the investigator |

Adverse events are not:

- continuous and persistent disease or symptom, present before the trial, which fails to
- signs or symptoms of the disease being studied.

Hospitalisations for treatment planned prior to randomisation and hospitalisation for elective treatment of a pre-existing condition will not be considered as an AE. Complications occurring during such hospitalisation will only be considered an AE or SAE if it is related to the trial interventions.

8.2 **Trial specific considerations**

In this trial, all related AEs will be recorded (see definition of "related" in section 8.3.2 below). All serious related AEs will be recorded as SAEs. All deaths (any cause) will also be recorded as SAEs.

Due to the reporting and collection of these events as primary and secondary outcome measures, the following do not need to be reported as AEs or SAEs:

- Pelvic floor symptoms including pelvic organ prolapse, urinary and colorectal-anal symptoms
- Sexual dysfunction

Furthermore, pre-existing conditions and any pre-planned hospitalisations (e.g. elective surgery) not associated with clinical deterioration will not be classed as Serious Adverse Events.

IRAS ID: 338183 PEPPY protocol version 3.0 26/02/2025 **ISRCTN: xxxxxx** Page 24 of 51

PEPPY specific expected adverse events:

The PEPPY trial involves interventions to treat pelvic organ prolapse which are well established in clinical practice. Expected adverse events (although unlikely) arising from PFMT and pessary usage are:

- Pelvic floor muscle soreness
- Low back pain
- Vaginal irritation/discomfort
- Granulation of vaginal tissue
- Involuntary expulsion of pessary
- Vaginal smell
- Vaginal discharge
- Vaginal infection
- Vaginal bleeding
- Psychological distress due to vaginal assessment (e.g. as a result of previous abuse or distressing labour)
- Pessary entrapment in the vagina requiring removal in theatre
- Urinary retention requiring catheterisation
- Faecal impaction requiring hospital intervention
- Fistula: recto-vaginal or vesico-vaginal
- Vaginal cancer
- Ureteric obstruction

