A vaginal pessary will be fitted after the participant has completed the baseline questionnaire and been randomised (usually both will occur at the baseline/first PFMT appointment), in accordance with usual practice at the participating centre. There will be no restriction on pessary type, and women may be offered to self-manage their pessary if this option is available at their centre [21]. The type and size of pessary a woman uses will be recorded and reported. Pessary care will be delivered by a clinician (usually a gynaecologist, nurse or physiotherapist, depending on the service model at each centre) with specialist training in fitting and managing vaginal pessaries. Participants will be asked to use the pessary for at least 16 weeks (during the period of supervised PFMT) but can continue to use it if desired. Pessary review appointments will be offered to participants with the frequency dependent on whether they are self-managing or not. Participants who self-manage their pessary (who can remove the pessary themselves) will be asked to remove the pessary and those who do not self-manage will be asked to come to clinic to have the pessary removed 2 weeks before they receive their 6 and 12 month questionnaires. Participants will record details of their pessary use (insertion, removal, replacement, complications) in a diary (alongside their PFMT exercise recordings). Participants continuing pessary use after their time in the trial will receive care via their centre's usual pessary service.

An initial programme theory has been developed, proposing the pathway between intervention and outcome (Figure 1). The hypothesised mechanism of action is that successful pessary use will anatomically correct the prolapse. The anatomical correction will enable a more effective pelvic floor contraction which will lead to a greater improvement in prolapse symptoms than PFMT alone. Contextual factors suggested by previous evidence and theory to influence the pathway to outcome are included in the programme theory. Specifically, the outer circle signifies that intervention delivery, and outcomes are all influenced by context [22]. The nature of the

IRAS ID: 338183 PEPPY protocol version 3.0 26/02/2025 ISRCTN: xxxxxx Page 19 of 51

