6.2 Secondary outcome measures

Secondary outcomes include participant-reported pelvic floor dysfunction-related quality of life (QoL) measured using the Pelvic Floor Impact Questionnaire-7 (PFIQ-7) [23]. The PFIQ-7 was developed and validated in parallel with the PFDI-20 and includes questions on the effect of bladder (7 items), bowel (7 items) and prolapse (7 items) symptoms on activities, relationships and feelings. There are three subscales (UIQ-7, CRAIQ-7, POPIQ-7), with each sub-score ranging from 0-100, and the total score ranging from 0-300: higher scores reflect more impact on quality of life.

Other participant-reported secondary outcomes are general health-related QoL (EQ-5D-5L) (two-part instrument: five items on mobility, self-care, usual activities, pain/discomfort and anxiety/depression, plus the EQ-5D Visual Analogue Scale) [24]; Patient Global Impression of Improvement (PGI-I) (single-item participant rating of change in a condition since having treatment, validated for prolapse, with 7 responses from "very much better" to "very much

PEPPY protocol version 3.0 26/02/2025 **ISRCTN: xxxxxx** Page 20 of 51 worse") [25]; the ICIQ Vaginal Symptoms (ICIQ-VS) Sexual Matters subscale, with 4 items and score from 0 to 58, higher scores indicating worse sexual function [26]; uptake of other prolapse treatment (including surgery); self-efficacy for PFMT (Pelvic Floor Muscle Exercise Self-Efficacy Scale) [27]; and adherence to trial interventions (exercise/pessary use and experience diary).

An economic outcome, Quality Adjusted Life Years (QALYs), will be calculated from EQ-5D-5L data using the recommended tariff values [28].

Two clinical secondary outcomes are pelvic floor muscle strength and function (Modified Oxford Scale (MOS), 0 "no contraction" to 5 "strong (with lift) contraction", assessed via digital palpation) [29]; and prolapse severity (Pelvic Organ Prolapse Quantification (POP-Q) method, Stage I-IV) [20]. From our experience, use of the POP-Q system is challenging to implement in trials across many centres and different health professional groupings, therefore an experienced gynaecologist will be identified to undertake the POP-Qs at each centre.

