Outcomes will be measured at baseline, 6 months and 12 months (with the exception of pelvic floor muscle and prolapse severity assessments which take place at baseline and 12 months). Pessary use will be paused 2 weeks before the 6 and 12 month time-points for women in the PFMT plus pessary group, to allow the pelvic organs to reposition without the pessary support prior questionnaires being completed and (at 12 months) clinical assessment being carried out. We will record if women do not pause pessary use prior to assessment and use this information in a sensitivity analysis.

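### The adverse event exemption in section 8.2 relies on outcome questionnaires that are scheduled with the pessary out, so it does not cover non-serious symptoms confined to pessary wear

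*Protocol*

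**What the plan says.** Section 8.2 opens with a general rule: "In this trial, all related AEs will be recorded". It then sets aside two classes of event from both AE and SAE reporting, namely pelvic floor symptoms (prolapse, urinary and colorectal-anal) and sexual dysfunction, with this reason: "Due to the reporting and collection of these events as primary and secondary outcome measures, the following do not need to be reported". Section 8.1 separately says that AEs do not include "signs or symptoms of the disease being studied".

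The outcomes that carry these symptoms are mainly the PFDI-20 and the ICIQ-VS Sexual Matters subscale. Section 6.2 and Table 2 schedule them at baseline, 6 months and 12 months. Three statements fix where those time-points fall relative to wear:

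- Section 5.1, on baseline: "A vaginal pessary will be fitted after the participant has completed the baseline questionnaire and been randomised".
- Section 5.1, on duration: "Participants will be asked to use the pessary for at least 16 weeks", with longer use allowed.
- Section 6.2, on follow-up: "Pessary use will be paused 2 weeks before the 6 and 12 month time-points for women in the PFMT plus pessary group".

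Other contacts take place during wear. Under section 5.1, women keep a diary of pessary use that includes complications. Under section 7.2, the treating clinician reviews that diary at each PFMT appointment in order to record fidelity. Section 8.3.1 has staff ask about AEs at every appointment, limited to events that meet the trial's recording criteria, and it refers the reader to section 8.1 for those criteria.

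**The concern.** Leaving outcome events out of AE reporting is reasonable when the outcome measure captures them. Here the measure is timed to capture something else. The pause exists so that the 6 and 12 month scores reflect the pelvic floor without pessary support. That suits the efficacy question, and section 1.1 criticises the earlier single-site trial for having no such washout. A measurement designed to remove the pessary's direct effect cannot also stand in for recording the pessary's direct harms.

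The symptoms at issue are new leakage, voiding difficulty short of catheterisation, milder bowel symptoms, and painful intercourse to the extent that it is not recorded as vaginal discomfort. If centres take the exemption at face value, related symptoms of this kind could be missing from the safety data, mostly in the pessary arm. The tolerability cost of adding the device would then be understated. What is not recorded during wear cannot be recovered by later analysis.

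**Working it through.** The protocol gives no figure for this point that could be reproduced. The check compares the reason in section 8.2 with the outcome schedule.

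**1. Position of each symptom questionnaire**

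| Time-point | Pessary status if the protocol is followed | Source |
|---|---|---|
| Baseline | Not yet fitted | Section 5.1 |
| 6 months | Out for 2 weeks | Sections 5.1, 6.2, 7.4 |
| 12 months | Out for 2 weeks | Sections 5.1, 6.2, 7.4 |

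Baseline could never be on-pessary, so the fair count is 0 of 2 post-fitting questionnaires. Women who do not pause are an unplanned exception, recorded for a sensitivity analysis.

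**2. Length of the uncovered wear**

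Assume 6 months = 26 weeks and 12 months = 52 weeks from randomisation. Fitting takes place between week 0 and week 2 (randomisation section).

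- Longest wear before the 6-month questionnaire: 26 − 2 − 0 = 24 weeks, or 26 − 2 − 2 = 22 weeks.
- Longest wear between the 6 and 12 month questionnaires, if resumed at once: 52 − 2 − 26 = 24 weeks.
- The requested 16 weeks of wear therefore fall wholly before the first post-fitting questionnaire.

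**3. Recall needed for the 6-month questionnaire to reach wear**

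The protocol states no recall period for these instruments.

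| Woman | To reach any wear | To cover all wear |
|---|---|---|
| Wears until the pause at week 24 | More than 26 − 24 = 2 weeks | 24 to 26 weeks |
| Fitted week 0, stops at week 16 | More than 26 − 16 = 10 weeks | 26 − 0 = 26 weeks |
| Fitted week 2, stops at week 18 | More than 26 − 18 = 8 weeks | 26 − 2 = 24 weeks |

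Some retrospective capture is therefore possible, most easily in women who continue. The protocol does not settle how much.

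**4. Routes open during wear, and whether they lead to AE recording**

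- Diary (sections 5.1, 6.2, 7.2): complications can be entered and a clinician sees them. The diary serves the adherence outcome, and the stated purpose of the review is fidelity. No instruction carries entries to the AE form.
- AE enquiry (section 8.3.1): takes place at every appointment, but only for events meeting the recording criteria. An exempted symptom can be read as failing them.
- Expected events (section 8.2): vaginal effects are listed, but retention only if catheterised and impaction only if it needs hospital intervention. Milder forms are not named.
- One-week fitting check (section 9.2) and open question at 6 and 12 months (section 12.2.4): neither is tied to AE recording.

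**5. Number exposed**

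Section 9.1 plans for 40% fitting non-success, so 276 × 0.60 = 165.6, about 166 women wearing the pessary. The symptom frequency is not in the protocol. For scale, each 1% of women affected is 1.66 of 166, or 2.76 if all 276 have at least brief wear.

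**The case against.** The strongest reply is that symptoms during wear do not go unseen. A clinician holding a diary with a complications entry must also ask about AEs at that same appointment, and a fidelity purpose for the diary review does not prevent that. The resource-use questionnaire (section 11.2) covers the time since the previous one and would trace symptoms that led to care. Many device effects are named as expected AEs: irritation, discharge, bleeding, infection, expulsion and the severe urinary and bowel events. Avoiding double-counting of outcome events is a defensible policy for treatments already routine in the NHS. CRFs and AE guidance, where prompts would usually sit, are not shown.

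Much of this stands, and it limits the point. A reader might infer that symptoms during wear are simply not collected; the diary and the AE enquiry show otherwise. A reader might also infer that section 8.2 contradicts itself, promising to record all related AEs and then exempting some. The protocol does not establish that: the exempting phrase is permissive, and recording and reporting are handled in separate subsections (8.3.3 and 8.3.4), although the latter concerns SAEs. The pointer in section 8.3.1 to 8.1 rather than 8.2 looks like a cross-reference slip.

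What the reply does not supply is a sentence that brings these symptoms into AE recording. It also does not rescue the reason given, because the diary is an adherence measure and service use is not a symptom outcome.

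**Conclusion.** The point holds in a limited form. The stated reason for the exemption fails for new or worsened non-serious urinary, bowel or sexual symptoms confined to wear, because neither post-fitting symptom questionnaire is scheduled with the pessary in place. Routes to notice such symptoms exist, but none is directed to AE recording, and two centres could reasonably treat the same pessary-related leakage differently.

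The number of women affected cannot be stated. It depends on symptom frequency, on recall periods and on how centres read the exemption. The week counts rest on 26- and 52-week follow-up counted from randomisation.

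This is a gap in safety capture. It does not affect the primary analysis or the sample size, and it does not extend to the severe urinary and bowel events that the protocol names as expected AEs. Severity is minor to moderate.

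**What to change.** In section 8.2, state that the exemption does not apply to new or worsened urinary, bowel or sexual symptoms that arise during pessary wear or PFMT and are judged related. Record these as AEs from the existing AE enquiry and diary review, asked in the same way in both arms. Note any such symptom given as the reason for removing or stopping the pessary, and list these descriptively, since only the pessary arm can have them. In section 8.1, say that the exclusion of disease symptoms does not cover symptoms attributed to the pessary. In section 8.3.1, refer to 8.2 as well as 8.1. The policy of recording only related AEs is unchanged.

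The cost is a wording amendment and no extra visit. Each added AE needs three judgements (seriousness, relatedness, expectedness) from unblinded staff; per 1% of 166 wearers affected with one event each, that is 1.66 × 3, about 5 assessments, with any control-arm records on top. Some difference in ascertainment will remain, because pessary reviews give that arm more contacts; this should be stated when the AE data are reported.

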6.1 Primary outcome measure

Our primary outcome measure is participant-reported symptoms of pelvic floor dysfunction measured using the Pelvic Floor Dysfunction Inventory-20 (PFDI-20) [29] at 12 months. PFDI-20 measures the severity of pelvic floor-related symptoms. It contains 20 questions about the presence of prolapse (6 items), bladder (6 items) and bowel (8 items) symptoms, and how bothersome these are, with three respective subscales (UDI-6, CRADI-8, POPDI-6). Each subscore ranges from 0-100 and the total score from 0-300: higher scores reflecting more bothersome symptoms.

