8.3.4 Reporting SAEs

Reporting responsibilities of centres

Once the local Investigator becomes aware that an SAE has occurred in a trial participant, they must report the information to the Trial Office/Chief Investigator within 24 hours of becoming aware of the event as per the Sponsor guidance.

The SAE form must be completed as thoroughly as possible with all available details of the event and signed by the local Investigator or designee. If all the required information is not available at the time of reporting, the Investigator must ensure that any missing or follow-up information is provided as soon as this becomes available. It should be indicated on the report that this information is follow-up information of a previously reported event.

To report an SAE to the Trial Office, centre staff can either complete a hard copy of the SAE form and email it to the Trial Office or upload the SAE onto the trial website. If the SAE form is uploaded onto the trial website, the Trial Manager will be automatically notified.

If, in the opinion of the local PI and/or the CI, the event is confirmed as being serious but not related, or serious, related and expected, expedited reporting to Sponsor is not required. Rather these will be summarised and reported to Sponsor, REC, Funder, TSC and DMEC in their regular progress reports. Only expedited if serious, related and not expected event.

Reporting responsibilities of the Trial Office

The Trial Office will notify the Sponsor within 24 hours of receiving the signed SAE notification if the event is serious, related and not expected.

The sponsor will provide an assessment of the SAE. A Sponsor cannot downgrade an assessment from the local PI or CI. Any disparity will be resolved by further discussion between these parties and documented in the TMF.

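### The symptom exemption in Section 8.2 has no seriousness limit and leaves two listed complications undecided, and Section 8 gives no consistent recording rule for non-fatal unrelated SAEs

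*Protocol*

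**What the plan says.** All of this is in Section 8 of the protocol (version 3.0).

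**Exemption (8.2).** The reason given is that the events are collected as primary and secondary outcomes. On that ground "the following do not need to be reported as AEs or SAEs", and the first item is "Pelvic floor symptoms including pelvic organ prolapse, urinary and colorectal-anal symptoms". The second is sexual dysfunction. Neither item is limited by severity, seriousness or relatedness.

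**Expected events (8.2).** The list that follows the exemption has 16 entries. Two are urinary or bowel complications defined by the care they need: "Urinary retention requiring catheterisation" and "Faecal impaction requiring hospital intervention".

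**Recording rule (8.2).** "In this trial, all related AEs will be recorded", and "All serious related AEs will be recorded as SAEs". Deaths of any cause are recorded as SAEs too, and 8.3.3 repeats this.

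**Elsewhere in Section 8.** Section 8.3.1 refers the reader to 8.1 for the recording criteria. Section 8.3.4 asks centres to report an SAE within 24 hours of awareness. It says that when "the event is confirmed as being serious but not related", expedited reporting to the sponsor is not needed and the event goes into the regular reports to the sponsor, REC, funder, TSC and DMEC. Section 8.3.5 says that all SAEs are summarised to the REC, funder, TSC and DMEC.

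**The concern.** There are two separate problems.

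The first is that the exemption reaches SAEs while its justification does not. Leaving a symptom off the AE form is reasonable when a questionnaire already measures it. That argument fails for a symptom that becomes serious, because no outcome measure records the intervention or the admission. With two such complications also on the expected list, centres have two rules and no order of precedence, and capture may differ between centres.

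The second is that the sections disagree on whether a non-fatal serious event judged unrelated is recorded at all. This matters more than usual here. Relatedness is a yes/no judgement by the local investigator (8.3.2), treating staff cannot be blinded (4.8), and only one arm adds a device. If recording depends on that judgement, attribution could differ by arm, and an event that was never recorded cannot be looked at again by the DMEC, which oversees participant safety.

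**Working it through.** No figure in the plan depends on this point, so there is nothing to recompute. The check sets the passages side by side.

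**Step 1: does the outcome measure cover what is exempted?** Section 6.1 says "PFDI-20 measures the severity of pelvic floor-related symptoms". Its 20 items ask whether prolapse, bladder and bowel symptoms are present and how bothersome they are. Table 2 places it at baseline, 6 and 12 months. A woman catheterised at month 3 would contribute a symptom score at month 6, with nothing in that score to show the catheterisation. The reason for the exemption therefore holds for symptoms as scored, and not for an event defined by an intervention.

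**Step 2: how many listed events does the overlap touch?** The expected list has 16 entries. Two are explicitly urinary or bowel events needing intervention: 2/16. Whether they fall under the exemption depends on whether a complication counts as a symptom, which the protocol does not say. Section 8.1 adds that signs or symptoms of the disease under study are not AEs, a second ground on which a centre might leave such an event out.

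**Step 3: follow four kinds of event through Section 8.**

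| Event | 8.2 | 8.3.1, via 8.1 | 8.3.4 and 8.3.5 | Result |
|---|---|---|---|---|
| Related, serious, not urinary or bowel | Recorded | Recorded | Reported and summarised | Consistent |
| Death judged unrelated | Recorded | Recorded | Summarised | Consistent |
| Related, serious, urinary or bowel | Recorded under the recording rule; may be left out under the exemption; two such events are on the expected list | Recorded, unless treated as a symptom of the disease | Reported and summarised if treated as an SAE | Undecided |
| Non-fatal, serious, judged unrelated | Not recorded | Recorded: 8.1 has no general relatedness limit | 24-hour report has no relatedness limit; summary promised | Conflict |

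The only mention of relatedness in 8.1 concerns complications during hospital stays that are planned or elective. The general restriction to related events is in 8.2, so the cross-reference in 8.3.1 sends the reader to the wrong section.

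**Step 4: what the two faulty rows have in common.** In both, a centre can follow one sentence of Section 8 and depart from another. In the last row, the regular reports cannot reliably contain events that 8.2 does not ask centres to record.

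**The case against.** The strongest reply has four parts.

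- **The exemption says symptoms.** Retention and impaction are listed as complications defined by an intervention, and listing them as expected AEs just after the exemption suggests that they are meant to be reported. This is a fair reading, so a reader who infers a flat contradiction goes too far. What stands is an overlap that the text does not resolve.
- **Unrelated deaths are recorded.** It is tempting to say that only related SAEs are kept, or that the DMEC sees only attributed events. Sections 8.2 and 8.3.3 rule that out. The category of serious but unrelated events in 8.3.4 is not empty: it holds unrelated deaths, and events that a centre reports and that are later judged unrelated. All SAEs in 8.3.5 can be read as all those recorded. The gap is confined to non-fatal unrelated SAEs.
- **Related-only recording is a legitimate choice.** Section 1.3 ties reporting to the risk assessment and notes that both treatments, alone and combined, are in routine NHS use. This stands. The fault is inconsistent application, not the choice.
- **Other channels exist.** Staff ask about events at every contact (8.3.1), pessary complications go into a diary (5.1), and the resource-use questionnaire covers inpatient and emergency care (11.2). It therefore does not follow that serious events will go unseen. But the 8.3.1 enquiry covers only events that meet the recording criteria, which are the point in dispute, and Section 8 gives the diary and the resource-use questionnaire no role in safety reporting.

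The relatedness judgement is also not left wholly to local staff: 8.3.4 allows for the chief investigator's opinion and a sponsor assessment that cannot downgrade. Both come after an event has been reported.

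**Conclusion.** The point holds in two limited parts. First, a centre following the exemption as written could omit a related serious urinary or bowel event that no outcome measure captures; the expected list names two candidates among its 16 entries and does not settle the matter. Second, non-fatal SAEs judged unrelated have no consistent recording rule across 8.2, 8.3.1, 8.3.4 and 8.3.5.

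The size in events cannot be given, because the protocol states no rates of retention, impaction or all-cause hospitalisation. The first part assumes that some centres would count these complications as symptoms, which the text allows but does not require. Whether a particular case is serious under 8.1 would be decided case by case.

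A reader might also infer that the between-arm safety comparison is biased. The protocol does not support that as a finding: Section 10 specifies no such comparison, its tabulation may properly sit in the SAP, and neither size nor direction of any bias can be derived. Differential attribution is a possibility that the unblinded design leaves open.

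The change should be made. It is cheap, and it improves the capture of serious events.

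**What to change.** 1. **Limit the exemption in 8.2** to non-serious symptoms captured by PFDI-20 or the ICIQ-VS subscale. State that related events meeting an 8.1 seriousness criterion, including the two listed complications, are reportable despite the exemption.
2. **Correct the cross-reference in 8.3.1** so that it points to 8.2 for the recording criteria.
3. **State one rule for non-fatal unrelated SAEs** and apply it in 8.2, 8.3.4 and 8.3.5. Either record them with relatedness as a field on the form, or keep related-only recording and limit the promised summaries to recorded SAEs and deaths. Both are coherent; the sponsor should choose one.

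There is no need to record every entry on the expected list regardless of relatedness. The list includes common complaints such as low back pain and vaginal discharge, and doing so would overturn the related-only rule for AEs.

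The cost is wording in Section 8, guidance for the SAE form, and some extra SAE forms. Their number cannot be estimated from the protocol. It would be larger if unrelated SAEs are recorded, since non-fatal hospitalisations in 552 women over 12 months would then count, apart from the planned or elective admissions that 8.1 and 8.2 leave out.
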